3.4.2 Assessing and Recording Adverse Events

An adverse event is defined as any untoward medical occurrence in a patient or clinical investigation subject administered a pharmaceutical product and which does not necessarily have to have a causal relationship with this treatment. An adverse event can therefore be any unfavourable and unintended sign (including an abnormal laboratory finding, for example), symptom, or disease temporally associated with the use of a medicinal product or protocol-specified procedure, whether or not considered related to the medicinal product or protocol-specified procedure. Any worsening (i.e., any clinically significant adverse change in frequency and/or intensity) of a preexisting condition that is temporally associated with the use of the Sponsor's product, is also an adverse event.

Changes resulting from normal growth and development that do not vary significantly in frequency or severity from expected levels are not to be considered adverse events. Examples of this may include, but are not limited to, teething, typical crying in infants and children and onset of menses or menopause occurring at a physiologically appropriate time.

Sponsor's product includes any pharmaceutical product, biological product, device, diagnostic agent or protocol-specified procedure, whether investigational (including placebo or active comparator medication) or marketed, manufactured by, licensed by, provided by or distributed by the Sponsor for human use.

Adverse events may occur during the course of the use of the Sponsor's product in clinical trials or within the follow-up period specified by the protocol, or prescribed in clinical practice, from overdose (whether accidental or intentional), from abuse and from withdrawal.

Adverse events may also occur in screened subjects during any pre-allocation baseline period as a result of a protocol-specified intervention, including washout or discontinuation of usual therapy, diet, placebo treatment or a procedure.

All adverse events will be collected from the time the consent form is signed through 14 days following the first vaccination(s) and from the time of any subsequent vaccination(s) through 14 days thereafter, and such events will be recorded at each examination on the Adverse Event case report forms/worksheets.

3.4.2.1 Definition of an Overdose for This Protocol and Reporting of Overdose to the Sponsor

In this trial, an overdose is any dose higher than 0.75 mL of vaccine in any one dose or receiving >4 doses (0.5mL each dose).

If an adverse event(s) is associated with ("results from") the overdose of Sponsor's product or vaccine, the adverse event(s) is reported as a serious adverse event, even if no other seriousness criteria are met.

If a dose of Sponsor's product or vaccine meeting the protocol definition of overdose is taken without any associated clinical symptoms or abnormal laboratory results, the overdose is reported as a non-serious Event of Clinical Interest (ECI), using the terminology "accidental or intentional overdose without adverse effect."

All reports of overdose with and without an adverse event must be reported within 24 hours to the Sponsor either by electronic media or paper. Sponsor Contact information can be found in the Investigator Trial File Binder.

3.4.2.2 Reporting of Pregnancy and Lactation to the Sponsor

Although not considered an adverse event, it is the responsibility of the investigators or their designees to report any pregnancy in a subject (spontaneously reported to them or detected by urine or serum pregnancy test per protocol) that occurs during the trial through 1 month following the last vaccination. If a subject becomes pregnant during the trial, including subjects who never received vaccine allocation and had a positive pregnancy test at Day 1, all related information must be reported to the SPONSOR. For subjects who become pregnant with LMP prior or equal to Day 30 following the final vaccination, the pregnancy will be collected in the SPONSOR'S global safety database. Furthermore, all fetal loss pregnancy outcomes (ectopic pregnancy, elective termination, spontaneous abortion, late fetal death) must be reported as a

Serious Adverse Experience (Other Important Medical Event). All subjects who receive study vaccine, including discontinued subjects who agree to provide further information, must be followed to the completion/termination of the pregnancy. In addition, if the pregnancy continues to term, the outcome (health of the infant) must be reported.

If a subject receives study vaccine while breastfeeding all related information, including outcome, must be reported to the SPONSOR. Infant serious adverse experiences (SAEs) for all infants born to subjects who received study vaccine must be reported to the SPONSOR.

All pregnancy, lactation, and infant SAE events must be reported within 24 hours to the SPONSOR either by electronic media or paper. SPONSOR contact information can be found in the Investigator Trial File Binder. Refer to Data Entry Guidelines (DEGs) for instructions for reporting these events.

3.4.2.3 Immediate Reporting of Adverse Events to the Sponsor

3.4.2.3.1 Serious Adverse Events

A serious adverse event is any adverse event occurring at any dose or during any use of Sponsor's product that:

- Results in death;
- Is life threatening;
- Results in persistent or significant disability/incapacity;
- Results in or prolongs an existing inpatient hospitalization;
- Is a congenital anomaly/birth defect;
- Is a cancer;
- Is associated with an overdose;
- Is another important medical event

Refer to [Table 4](#) for additional details regarding each of the above criteria.

Any serious adverse event, or follow up to a serious adverse event, including death due to any cause, that occurs to any subject from the time the consent is signed through 1 month following the last vaccination, whether or not related to the Sponsor's product, must be reported within 24 hours to the Sponsor either by electronic media or paper. Sponsor Contact information can be found in the Investigator Trial File Binder.

Additionally, any serious adverse event brought to the attention of an investigator who is a qualified physician at any time outside of the time period specified in the previous paragraph also must be reported immediately to the Sponsor if the event is either:

- A death that resulted in the subject discontinuing the trial
 - or
- A serious adverse event that is considered by an investigator who is a qualified physician to be vaccine related.

All subjects with serious adverse events must be followed up for outcome.

3.4.2.3.2 Events of Clinical Interest

Selected non-serious and serious adverse events are also known as Events of Clinical Interest (ECI) and must be recorded as such on the Adverse Event case report forms/worksheets and reported within 24 hours to the Sponsor either by electronic media or paper. Sponsor Contact information can be found in the Investigator Trial File Binder.

Events of clinical interest for this trial include:

- An overdose of Sponsor's product, as defined in Section 3.4.2.1- Definition of an Overdose for This Protocol and Reporting of Overdose to the Sponsor, that is not associated with clinical symptoms or abnormal laboratory results.

3.4.2.4 Evaluating Adverse Events

An investigator who is a qualified physician will evaluate all adverse events with respect to the elements outlined in [Table 4](#). The investigator's assessment of causality is required for each adverse event. Refer to [Table 4](#) for instructions in evaluating adverse events.

Table 4 Evaluating Adverse Events

Maximum Intensity	Mild	awareness of sign or symptom, but easily tolerated (for pediatric trials, awareness of symptom, but easily tolerated)
	Moderate	discomfort enough to cause interference with usual activity (for pediatric trials, definitely acting like something is wrong)
	Severe	incapacitating with inability to work or do usual activity (for pediatric trials, extremely distressed or unable to do usual activities)
Seriousness	Injection site redness or swelling from the day of vaccination through Day 4 post-vaccination will be evaluated by maximum size.	
	A serious adverse event (AE) is any adverse event occurring at any dose that:	
	† Results in death; or	
	† Is life threatening; or places the subject, in the view of the investigator, at immediate risk of death from the event as it occurred [Note: This does not include an adverse event that, had it occurred in a more severe form, might have caused death.]; or	
	† Results in a persistent or significant disability/incapacity (substantial disruption of one's ability to conduct normal life functions); or	
	† Results in or prolongs an existing inpatient hospitalization (hospitalization is defined as an inpatient admission, regardless of length of stay, even if the hospitalization is a precautionary measure for continued observation. (Note: Hospitalization [including hospitalization for an elective procedure] for a preexisting condition which has not worsened does not constitute a serious adverse event.); or	
	† Is a congenital anomaly/birth defect (in offspring of subject taking the product regardless of time to diagnosis); or	
	Is a cancer; or	
	Is associated with an overdose (whether accidental or intentional). Any adverse event associated with an overdose is considered a serious adverse event. An overdose that is not associated with an adverse event is considered a non-serious event of clinical interest and must be reported within 24 hours.	
	Other important medical events that may not result in death, not be life threatening, or not require hospitalization may be considered a serious adverse event when, based upon appropriate medical judgment, the event may jeopardize the subject and may require medical or surgical intervention to prevent one of the outcomes listed previously (designated above by a †).	
Duration	Record the start and stop dates of the adverse event. If less than 1 day, indicate the appropriate length of time and units	
Action taken	Did the adverse event cause the test vaccine to be discontinued?	
Relationship to test vaccine	Did the test vaccine cause the adverse event? The determination of the likelihood that the test vaccine caused the adverse event will be provided by an investigator who is a qualified physician. The investigator's signed/dated initials on the source document or worksheet that supports the causality noted on the AE form, ensures that a medically qualified assessment of causality was done. This initialed document must be retained for the required regulatory time frame. The criteria below are intended as reference guidelines to assist the investigator in assessing the likelihood of a relationship between the test vaccine and the adverse event based upon the available information. The following components are to be used to assess the relationship between the test vaccine and the AE; the greater the correlation with the components and their respective elements (in number and/or intensity), the more likely the test vaccine caused the adverse event:	
	Exposure	Is there evidence that the subject was actually exposed to the test vaccine such as: reliable history, acceptable compliance assessment (e.g., diary), seroconversion or identification of vaccine virus in bodily specimen?
	Time Course	Did the AE follow in a reasonable temporal sequence from administration of the test vaccine? Is the time of onset of the AE compatible with a vaccine-induced effect?
	Likely Cause	Is the AE not reasonably explained by another etiology such as underlying disease, other drug(s)/vaccine(s), or other host or environmental factors

Relationship to test vaccine (continued)	The following components are to be used to assess the relationship between the test vaccine and the AE: (continued)	
	Dechallenge	(not applicable for vaccines)
	Rechallenge	Was the subject reexposed to the test vaccine in this trial? If yes, did the AE recur or worsen? If yes, this is a positive rechallenge. If no, this is a negative rechallenge. (Note: This criterion is not applicable if: (1) the initial AE resulted in death or permanent disability, or (2) the trial is a single-dose vaccine trial.) NOTE: IF A RECHALLENGE IS PLANNED FOR AN ADVERSE EVENT WHICH WAS SERIOUS AND WHICH MAY HAVE BEEN CAUSED BY THE TEST VACCINE, OR IF REEXPOSURE TO THE TEST VACCINE POSES ADDITIONAL POTENTIAL SIGNIFICANT RISK TO THE SUBJECT, THEN THE RECHALLENGE MUST BE APPROVED IN ADVANCE BY THE U.S. CLINICAL MONITOR AND THE INSTITUTIONAL REVIEW BOARD/INDEPENDENT ETHICS COMMITTEE.
	Consistency with Trial Vaccine Profile	Is the clinical/pathological presentation of the AE consistent with previous knowledge regarding the test vaccine or vaccine class pharmacology or toxicology?
The assessment of relationship will be reported on the case report forms /worksheets by an investigator who is a qualified physician according to his/her best clinical judgment, including consideration of the above elements.		
Record one of the following:	Use the following criteria as guidance (not all criteria must be present to be indicative of a vaccine relationship).	
Yes, there is a reasonable possibility of vaccine relationship.	There is evidence of exposure to the test vaccine. The temporal sequence of the AE onset relative to the administration of the test vaccine is reasonable. The AE is more likely explained by the test vaccine than by another cause.	
No, there is not a reasonable possibility of vaccine relationship	Subject did not receive the test vaccine OR temporal sequence of the AE onset relative to administration of the test vaccine is not reasonable OR there is another obvious cause of the AE. (Also entered for a subject with overdose without an associated AE.)	

3.4.2.5 Sponsor Responsibility for Reporting Adverse Events and Patient/Device Events and Incidents

All Adverse Events will be reported to regulatory authorities, IRB/IECs and investigators in accordance with all applicable global laws and regulations.

3.5 Statistical analysis plan

This section outlines the statistical analysis strategy and procedures for the study. If, after the study has begun, but prior to database lock, changes are made to primary hypotheses, or the statistical methods related to those hypotheses, then the protocol will be amended (consistent with International Conference on Harmonisation [ICH] Guideline E-9). Changes to exploratory or other non-confirmatory analyses made after the protocol has been finalized, along with an explanation as to when and why they occurred, will be listed in the clinical study report (CSR) for the study. Post hoc exploratory analyses will be clearly identified in the CSR. All statistical analyses specified in this protocol will be conducted using SAS® Version 9.3 or higher.

3.5.1 In-house Blinding

All subjects in this study will receive GARDASIL®9; the study is thus open-label. However, laboratory personnel conducting HPV assays will be blinded to all subjects' age.

3.5.2 Hypothesis/Estimation

Objectives and hypotheses of the study are stated in Section 2.1.

The study will be considered a success if the non-inferiority criteria for GMTs are met for HPV types 16, 18, 31, 33, 45, 52, and 58 for the comparisons between 27- to 45-year-old women versus 16- to 26-year-old women that received GARDASIL®9.

3.5.3 Analysis Endpoints

3.5.3.1 Immunogenicity

The primary immunogenicity endpoints are the cLIA GMTs to HPV 16, 18, 31, 33, 45, 52 and 58 at 4 weeks after Dose 3.

The secondary immunogenicity endpoints are:

the cLIA seroconversion percentages to HPV 16, 18, 31, 33, 45, 52 and 58 by 4 weeks after Dose 3 in 27- to 45-year-old women.

the cLIA GMTs and the cLIA seroconversion percentages to each of HPV 6, 11, 16, 18, 31, 33, 45, 52, and 58 by 4 weeks after Dose 3 in 16- to 26-year-old women and 27- to 45-year-old women.

A subject with a cLIA titre at or above the serostatus cutoff for a given HPV type (see Section 3.3) is considered seropositive for that type. Seroconversion is defined as changing serostatus from seronegative at Day 1 to seropositive, by 4 weeks after Dose 3.

3.5.3.2 Safety

Safety assessment will focus on injection-site adverse reactions and elevated temperatures Day 1 to Day 5 post-vaccination and systemic AEs Day 1 to Day 15 post-vaccination, reported on the electronic VRC. In addition, SAEs and pregnancy will be collected from the time the ICF is signed through 1 month following the last vaccination.

3.5.4 Analysis Populations

3.5.4.1 Immunogenicity Analysis Populations

Per Protocol Immunogenicity Population

The per-protocol immunogenicity (PPI) analysis populations will serve as the primary populations of subjects for the analysis of immune responses to each of the 9 HPV types (6, 11, 16, 18, 31, 33, 45, 52, and 58). The PPI analysis populations are HPV type-specific, i.e., each HPV type has its own PPI analysis population. To be included in a particular HPV type-specific PPI analysis population, subjects must:

- Have received all 3 vaccinations of the correct dose of GARDASIL®9 within acceptable day ranges (See [Table 5](#)).
- Have evaluable serology results at Day 1 and Month 7 based on serum samples collected within acceptable day ranges (See [Table 6](#)).
- Be seronegative to the appropriate HPV type at Day 1.
- Have no protocol deviations that could interfere with the evaluation of subject's immune response to GARDASIL®9.

To be included in the PPI analysis population for HPV 6 and 11, subjects must be seronegative to both HPV 6 and 11 at Day 1. To be included in the PPI analysis population for any other vaccine HPV type, subjects need to be seronegative to that specific type at Day 1. The final determination of protocol deviation categories deemed as having potential to interfere with evaluation of immune response to GARDASIL®9 will be made prior to database lock and will be recorded in a separate study document.

Table 5 Acceptable Day Ranges for Vaccination Visits

Dose of 9vHPV Vaccine Scheduled for Injection	Protocol Specified Visit Window	Day Range for Inclusion in Statistical Analysis (Relative to Day 1[†])
Dose 1	Day 1 [†]	0
Dose 2	Month 2 ± 3 weeks	36 to 84
Dose 3	Month 6 ± 4 weeks	148 to 218
[†] Day 1 refers to the date when Dose 1 of the study vaccine is injected. For vaccinations after Day 1, the day ranges for inclusion in the statistical analysis are wider than the protocol-specified visit windows primarily to account for differences at the study sites in counting months (e.g., 1 calendar month versus 30 days versus 4 weeks).		
9vHPV, 9-valent human papillomavirus.		

Table 6 Acceptable Day Ranges for Collection of Serum Samples

Study Visit	Target Collection Day (Relative to Day 1[†])	Day Range for Inclusion in Statistical Analysis[†]
Day 1	0	-14 to 0 (Relative to Day 1) [‡]
Month 7	30 days after Dose 3	21 to 49 after Dose 3 [§]
[†] Day 1 refers to the date when dose 1 of study vaccine is injected. For Month 7, indicated target collection/day range is relative to date of injection of Dose 3 of study vaccine.		
[‡] Applies to both the PPI and ANSS analysis populations.		
[§] Applies to the PPI analysis population only. The day range for the ANSS analysis population is 21 to 105 days after dose 3.		
ANSS = All type-specific naïve subjects with serology; PPI = Per-protocol immunogenicity.		

All Type-Specific Naïve Subjects with Serology Population

A supportive immunogenicity analysis will be carried out on the all type-specific naïve subjects with serology (ANSS) analysis population. The ANSS analysis populations are HPV type-specific similar to the PPI analysis populations. To be included in these sets of subjects, subjects must:

- Have received all 3 vaccinations of GARDASIL®9;
- Have evaluable serology results at Day 1 and Month 7 based on serum samples collected within acceptable day ranges (See Table 6);
- Be seronegative to the appropriate HPV type at Day 1.

To be included in the ANSS analysis population for HPV 6 and 11, subjects must be seronegative to both HPV 6 and 11 at Day 1. To be included in the ANSS analysis population for any other vaccine HPV type, subjects need to be seronegative to that specific type at Day 1.

Unlike the PPI analysis populations, ANSS analysis populations will not exclude subjects who had protocol deviations deemed as having potential to interfere with evaluation of V503-004-02

15-Mar-2017

immune response to GARDASIL®9. In addition, no day ranges on the timing of the vaccination will be applied.

3.5.4.2 Safety Analysis Population

The all subjects as-treated (ASaT) analysis population, comprised of subjects who received at least 1 dose of GARDASIL®9 and had at least 1 study visit with safety follow-up, will be the primary population for safety analyses.

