1.7 Study Flow Chart

Visit Windows (a):	Consent Visit	2 months after Day 1, ±3 weeks	6 months after Day 1, ±4 weeks	3 to 7 weeks after Month 6
Event/Test	Day 1 (Visit 1)	Month 2 (Visit 2)	Month 6 (Visit 3)	Month 7 (Visit 4) (b)
Obtain informed consent form / assent	+			
Informed Consent for Future Biomedical Research	+			
Assign screening number	+			
Review inclusion/Exclusion criteria (c)	+			
Collect medical history (past year)	+			
Collect demographics	+			
Collect height and weight	+			
Update Medical History (new conditions not already recorded as medical history or adverse events (AEs)		+	+	+
Review medications and non-study vaccines (d)	+	+	+	+
Pregnancy test (serum or urine) (e)	+	+	+	+
Blood sample for anti-HPV antibody testing (including retention serum) (10 ml of blood each time) (f)	+			+
Blood (DNA) for Future Biomedical Research (j)	+			
Collect oral temperature (g)	+	+	+	

Visit Windows (a):	Consent Visit	2 months after Day 1, ±3 weeks	6 months after Day 1, ±4 weeks	3 to 7 weeks after Month 6
Event/Test	Day 1 (Visit 1)	Month 2 (Visit 2)	Month 6 (Visit 3)	Month 7 (Visit 4) (b)
Assign allocation number	+			
Perform vaccination (Intramuscular; prefer deltoid muscle of non-dominant arm; do not give in buttocks)	+	+	+	
Provide electronic vaccination report card (eVRC)	+			
Review and collect eVRC data (h)		+	+	+
Review AEs, clinical follow-up for safety (i)	+	+	+	+

(a) To calculate visit windows, assume 1 month equals 30 days and 1 week equals 7 days.
 (b) Whenever possible, when a subject discontinues/withdraws prior to study completion, all applicable activities scheduled for the final study visit should be performed at the time of discontinuation except for serum collection for HPV testing.
 (c) A physical examination may be performed during Visit 1 if deemed necessary by the investigator to assess eligibility criteria.
 (d) See Section 3.2.2.2 for details of documentation times and time period restrictions for medications and non-study vaccines. If other non-study vaccines are administered at any time during the study, they should not be administered in the same limb as the study vaccine and must be appropriately documented.

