 (e) The serum or urine pregnancy test will be performed per the manufacturer's instructions. A pregnancy test will be performed before administration of each dose of the study vaccine and at the final Month 7 visit on all subjects. The pregnancy test must be performed prior to serum collection for HPV testing at Day 1.
 (f) Blood sample for anti-HPV measurements must be collected prior to the first study vaccination. Serum must be shipped as specified by the Sponsor. The retention serum vial must remain at the study site until the Sponsor notifies the study site to ship the samples. Leftover main study serum sample will be stored for future biomedical research if the subject consents to the Future Biomedical Research.
 (g) If the subject has a fever (defined as an oral temperature of $\geq 37.8^{\circ}\text{C}$ or 100.0°F) within the 24-hour period prior to receiving a study vaccination, the subject should not receive study vaccine, and the vaccination visit should be rescheduled until after the fever has resolved. Oral temperature will be measured prior to each vaccination.
 (h) The investigator should instruct the subject to use the eVRC to document oral temperature in the evening after each study vaccination and daily, at the same time of day, for 4 days after each study vaccination. Additionally, injection-site and systemic adverse event(s) (AEs), concomitant medications, and concomitant vaccinations are to be documented in the eVRC starting after each study vaccination for a total of 15 days, including the day of vaccination (Day 1 to Day 15).
 (i) Observe subjects for at least 15 minutes after each vaccination for immediate untoward effects. Serious adverse events (SAEs), pregnancy events, and lactation events should be reported to the Sponsor's, within 24 hours. Adverse events and SAEs will be followed for 15 days and 30 days, respectively, after the last dose (i.e., after the third dose for subjects completing the vaccination schedule or after the last received dose in the event of the subject withdrawing).
 (j) Informed consent for future biomedical research samples must be obtained to collect the DNA sample.

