2.7.2 Safety Analyses

All subjects who received at least 1 dose of GARDASIL®9 and have safety follow-up data will be included in the analysis of safety. Statistical analyses of AEs will follow the 3-tiered analysis approach commonly used by the Sponsor/Vaccine Manufacturer when conducting safety assessments.

Tier 1 analysis compares between group difference by providing incidence summaries by each group, computing (incidence) risk differences and 95% CIs of risk differences between groups and computing p-values corresponding to tests of significance of the risk differences. P-values and 95% CIs for between-age-group differences in the percentage of subjects with events will be calculated using the Miettinen and Nurminen [20] method.

Tier-1 AEs in this study include:

- injection-site adverse reactions prompted for on the eVRC occurring Day 1 to Day 5 following any vaccination, and
- elevated temperatures ($\geq 37.8^{\circ}\text{C}$ or 100.0°F) from Day 1 to Day 5 following any vaccination.

Tier 2 analysis follows the Tier 1 analysis approach, except p-values are not computed.

Tier-2 AE summaries include:

- systemic AEs within 14 days following any vaccination occurring in $\geq 1\%$ of subjects in any group,
- injection-site adverse reactions not prompted for on the eVRC occurring Day 1 to Day 5 following any vaccination in $\geq 1\%$ of subjects in any group,
- SAEs occurring within 14 days (Day 1 to Day 15) following any vaccination,
- serious vaccine-related AEs observed at any time during the study, and
- severe injection-site adverse reactions Day 1 to Day 5 following any vaccination visit.

Tier-3 AEs include summaries (counts and percentages) by each age-group for any other AEs, including all injection-site adverse reactions occurring from Day 1 to Day 5 following each vaccination visit, all systemic AEs occurring within 14 days (Day 1 to Day 15) of each vaccination visit, and all SAEs occurring during the study and not included in the Tier-2 analysis.

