3.2.9 Management of Pregnant Subjects

All subjects will have a serum or urine pregnancy test performed before administration of each dose of the study vaccine and at the final Month 7 visit per the manufacturer's instructions.

Any subject with a positive pregnancy test at Day 1 will not be vaccinated and will not be allowed to participate in the study.

For subjects who become pregnant after receiving one or two study vaccinations, study visits and vaccinations will be paused until resolution of the pregnancy (e.g. term, elective termination, spontaneous abortion). Study visits and study vaccination in pregnancy subjects will be handled as described in [Table 3](#). Breastfeeding is not a contraindication to receiving study vaccinations. Pregnancy and breast-feeding in study subjects and infant serious adverse experiences (SAEs) must be reported as described in Section 3.4.

Table 3 Guidelines for Pregnant Subjects: Managing Study Visits and Study Vaccinations

Time When Pregnancy is Detected	Action
Day 1 (before first vaccination)	Do not vaccinate subject
Between Day 1 and Month 2 (After study vaccine dose 1 and before study vaccine dose 2 was administered)	
 • No scheduled visits until resolution of the pregnancy (e.g., term, elective termination, spontaneous abortion). • The Month 2 study vaccination should be administered at least 4 weeks following resolution of pregnancy and after normalization of β-hCG levels. • The Month 6 study vaccination should be administered 4 months after the Month 2 study vaccination. • The Month 7 visit should be conducted 1 month after the Month 6 study vaccination.
Between Month 2 and Month 6 (After study vaccine dose 2 and before study vaccine dose 3 was administered)	
 • No scheduled visits until resolution of the pregnancy (e.g., term, elective termination, spontaneous abortion). • The Month 6 study vaccination should be administered at least 4 weeks following resolution of pregnancy and after normalization of β-hCG levels. • The Month 7 visit should be conducted 1 month after the Month 6 study vaccination.
After Month 6 (After study vaccine dose 3 was administered)	
 • Continue with scheduled study visits during the pregnancy. • Safety follow-up will be conducted after resolution of the pregnancy (e.g., term, elective termination, spontaneous abortion).

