3.4 Safety Measurements

3.4.1 Clinical Measurements for Safety

All subjects will be observed for at least 15 minutes after each study vaccination for any untoward effects, including allergic reactions. This observation period will be documented in the subject's study chart.

Each subject will receive an electronic VRC at the Day 1, Month 2, and Month 6 study vaccination visits. On the eVRC, the subject or the subject's parent or guardian will be asked to

record oral temperature in the evening after each study vaccination and daily, at the same time of day, for 4 days after each study vaccination for the purpose of identifying febrile events. They will also be asked to record any injection-site reactions prompted in the eVRC, i.e., injection-site tenderness, swelling, or redness occurring after each study vaccination and daily for 4 days after each study vaccination (solicited injection-site reactions). In addition to injection-site reactions prompted in the eVRC, the subject or the subject's parent or guardian will be asked to assess the presence of other injection-site reactions and systemic AEs starting after each study vaccination for a total of 15 days. The subject or the subject's parent or guardian will be asked to record injection-site and systemic AEs, concomitant medications, and concomitant vaccinations on the eVRC.

The information on the eVRC should be generated only by the subject or the subject's parent or legal guardian.. The subject will be expected to bring the eVRC to the study site at the next scheduled visit. In case of hospitalization or visit to another physician, the subject or the subject's parent or legal guardian should be informed to contact the investigator immediately.

The study site personnel will review the data captured on the eVRC with the subject or subject's parent/legal guardian at Visit 2 through Visit 4.

All eVRC information will be recorded in the EDC system. The investigator/sub-investigator will determine causality of systemic AEs recorded on the eVRC using the guidelines given in Section 3.4.2.4 and will classify each event as an SAE or non-serious AE. If an oral temperature indicates a fever (defined as an oral temperature of $\geq 37.8^{\circ}\text{C}$ or 100.0°F), the AE of "fever" must be documented in the electronic case report forms (e-CRFs).

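### Could the two wordings of the safety population leave a vaccinated woman with a known serious event out of the safety tables?

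*Combined protocol and SAP*

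**What the plan says.** The safety population is described twice.

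- Section 2.7.2, part of the data analysis summary: "All subjects who received at least 1 dose of GARDASIL®9 and have safety follow-up data will be included in the analysis of safety".
- Section 3.5.4.2, the detailed definition of ASaT: "comprised of subjects who received at least 1 dose of GARDASIL®9 and had at least 1 study visit with safety follow-up". It does not define a visit with safety follow-up.

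The study flow chart (Section 1.7) has a row "Review AEs, clinical follow-up for safety" that is marked at all four visits, Day 1 included. Note (i) to that row begins: "Observe subjects for at least 15 minutes after each vaccination for immediate untoward effects". Section 3.4.1 requires this observation to be documented in the study chart.

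Safety information can also arrive without a visit. Section 3.4.2.3.1 makes reportable any serious adverse event (SAE) "that occurs to any subject from the time the consent is signed through 1 month following the last vaccination". Section 3.4.1 adds: "In case of hospitalization or visit to another physician, the subject or the subject's parent or legal guardian should be informed to contact" the investigator at once. For a pregnancy found after a first or second dose, Table 3 in Section 3.2.9 begins: "No scheduled visits until resolution of the pregnancy (e.g., term, elective termination, spontaneous abortion"). Section 3.4.2.2 says that "all fetal loss pregnancy outcomes (ectopic pregnancy, elective termination, spontaneous abortion, late fetal death) must be reported as a" serious event.

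**The concern.** Having data and having attended a visit are different conditions. If the visit in Section 3.5.4.2 must come after the vaccination visit, inclusion depends on coming back. Death or a serious event can prevent that, so the few women left out could be left out because of their outcome. Table 7 tabulates deaths and serious vaccine-related events for any time during the study. A known event could then be missing from the primary population's table, although Section 2.7.2 would include the woman.

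The interval is long enough to make the case conceivable, since Visit 2 takes place well after the Day 1 to Day 15 reporting period has closed. The pause in visits during pregnancy seems to offer a concrete route. Comparing safety between the age groups is a secondary objective, so the composition of this population matters.

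**Working it through.** **1. Which reading does the text support?**

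| Question | Day 1 counts | A later visit is required |
|---|---|---|
| Text in support | Flow chart row marked at Day 1; note (i); documentation under Section 3.4.1 | None; inferred because the visit condition would otherwise do little |
| Who is left out of ASaT | Essentially nobody who was vaccinated and observed | Vaccinated women with no later visit |
| Agreement with Section 2.7.2 | Practically the same set | Differs for non-returners with a known event |

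**2. How long is the exposed interval?** Flow chart note (a) sets 1 month = 30 days and 1 week = 7 days. Visit 2 therefore falls between 60 − 21 = 39 and 60 + 21 = 81 days after Day 1. Day 15 is 14 days after vaccination, so the gap before Visit 2 can open is 39 − 14 = 25 days. These figures describe visit spacing, not lost data. A woman with an event in this interval who attends any later visit is in ASaT on either reading.

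**3. The pregnancy route.** Table 3 suspends visits only until the pregnancy resolves. The remaining vaccinations and the Month 7 visit then resume. A fetal loss is itself a resolution, so it ends the pause. Even on the strict reading the woman is lost only if she then never returns.

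**4. The plan's own figures.** Section 3.5.7.1.1 uses the 1,200 vaccinated women. With P = 1 − (1 − p)^1200:

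| True rate p | Plan | Recomputed |
|---|---|---|
| 1.0% | 99% | 99.999% |
| 0.5% | 99% | 99.76% |
| 0.1% | 70% | 69.9% |
| 0.05% | 45% | 45.1% |
| 0.01% | 11% | 11.3% |

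The zero-event statement also holds. At p = 0.39%, P = 99.08%, and the exact 99% bound is 1 − 0.01^(1/1200) = 0.383%.

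**5. Sensitivity on the strict reading.** The documents give no non-return rate, so I assume 0 to 60 of 1,200.

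| Non-returners | n | P at p = 0.1% | 99% bound |
|---|---|---|---|
| 0 | 1,200 | 69.9% | 0.383% |
| 12 | 1,188 | 69.5% | 0.387% |
| 24 | 1,176 | 69.2% | 0.391% |
| 60 | 1,140 | 68.0% | 0.403% |

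**6. One lost event.** Assume one affected woman with the only such event in a group of 600. Her group's incidence goes from 1/600 = 0.167% to 0/599 = 0%. The Miettinen-Nurminen risk differences against 0/600, with 95% intervals, are:

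- 1/600 versus 0/600: 0.167 points (−0.471 to 0.938)
- 0/599 versus 0/600: 0.000 points (−0.637 to 0.638)

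**7. Would admitting any safety data, by any route, be better?** If Day 1 counts, it changes nothing. If Day 1 does not count, non-returners would enter only when they have a report to bring them in. Assume 12 non-returners in a group of 600, one of them with the group's only event. Incidence is then 1/(588 + 1) = 1/589 = 0.170%, against 1/600 = 0.167% with everyone counted. The bias is tiny, but entry now depends on having an event, which is the original complaint in mirror image.

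**The case for a change.** The best case for a change is that the two sentences do differ, that Section 3.5.4.2 never says whether Day 1 counts, and that a condition excluding nobody looks odd, so a programmer might take follow-up to mean a later visit. Any exclusion would then depend on outcome. Section 3.5.5.2 already uses denominators of subjects followed over the relevant period, so the visit condition is not needed to protect them. Section 3.5.5.3 requires reasons for exclusion from the per-protocol immunogenicity populations but states none for ASaT. Rewording would cost one sentence.

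The difference in wording stands, and so does the point about outcome dependence on the strict reading. The consequence is much weaker:

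- A near-redundant condition is ordinary in a definition of this kind and does not override a flow chart that places safety follow-up at Day 1.
- Section 2.7.2 remains in use when ASaT is applied, because Section 3.5.5.2 refers back to it. Its third tier covers SAEs during the study that are not in the second tier.
- Section 3.5.5.2 commits to reviewing all collected safety data and summarising all adverse events whatever their incidence. These statements name no population, so they mitigate the point without settling it.
- Section 3.5.5.3 reports the number vaccinated by age group, so a shortfall in ASaT would be visible.
- Sections 3.2.14.1, 3.2.14.2 and 3.2.14.4 keep visits going after vaccination stops, ask for final-visit activities at withdrawal and require efforts to regain contact. A woman with no later visit should be rare.

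**Conclusion.** No change follows. The two descriptions differ in wording, but the reading with direct textual support counts the Day 1 visit. On it they select practically the same women and no known event is lost. This is a gap that analysts can fill sensibly from the flow chart.

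The conclusion rests on the Day 1 observation being carried out as scheduled and being treated as safety follow-up. On the strict reading the effect is confined to women who never return. Their number is unknown; 0 to 60 of 1,200 is my assumption. One lost event would move a group's incidence by 0.17 points, with both intervals including zero. The probability of seeing at least one event at a true rate of 0.1% would fall by at most 1.9 points (69.9% to 68.0%). Reporting of SAEs to the sponsor does not depend on ASaT. Table 9 and the 0.39% statement refer to all 1,200 vaccinated women and are correct as stated.
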